For each outcome construct (healthy relationship attitudes, healthy relationship behaviors, healthy financial attitudes, and healthy financial behaviors), we have identified the relevant survey measures that are theoretically aligned with that construct. When analysis begins, we will generate a correlation matrix between items in a given construct to ensure that theoretically related items are also empirically related in our data set. Survey items will be reverse-coded as needed before checking for correlation strength. Items that are not strongly correlated with other items in a construct will be removed as necessary. Factor analysis will be used to ensure that all construct items hang together, using an alpha of 0.7 or higher as the acceptable threshold. If a constructed scale does not achieve an alpha of 0.7 or higher, even after removing items that are not well correlated, the outcome measure will be dropped from the analysis.

We will then create a composite measure for each construct by taking an average of the scores on each non-missing item in the construct. For these composite measures, we intend to use 20% as a threshold for allowable missing items; this plan is contingent on the final distribution of missing data in our data set. Participants who are missing more than 20% of items for a given construct will be assigned a missing value for that composite outcome measure. We will not be imputing truly missing values for outcomes. To create the construct score for each participant, the average of the relevant survey items will be divided by the number of non-missing values in the construct.

Table 4. Outcomes used to answer the research questions

Research question	Outcome name	Description of the outcome measure	Source of the measure	Timing of measure
RQ1	Healthy relationship attitudes	The outcome measure is a scale (value range 1-4) calculated as the average of nine survey items related to healthy relationship beliefs	nFORM entrance survey (A1.a-i); nFORM exit survey	Wave 1 (before primary workshops begin) and Wave 2 (at the final primary workshop)
RQ1	Healthy relationship attitudes	The outcome measure is a scale (value range 1-5) calculated as the average of three survey items related to expectations that youth have for their future relationship circumstances	nFORM entrance survey (A2.a-c); nFORM exit survey	Wave 1 (before primary workshops begin) and Wave 2 (at the final primary workshop)

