RQ2	Healthy relationship behaviors	The outcome measure is a scale (value range 1-4) calculated as the average of five survey items related to reported self-assessed skill with communication and conflict resolution	nFORM entrance survey (C1b.a-e); OLLE follow-up survey	Wave 1 (before primary workshops begin) and Wave 3 (one year after program enrollment)
RQ2	Healthy relationship behaviors	The outcome measure is a scale (value range 1-5) calculated as the average of six survey items related to the frequency of engaging in unhealthy conflict resolution behaviors	nFORM entrance survey (C3.a-f); OLLE follow-up survey	Wave 1 (before primary workshops begin) and Wave 3 (one year after program enrollment)
RQ3	Healthy financial attitudes	The outcome measure is a scale (value range 1-5) calculated as the average of seven survey items related to level of agreement with key financial attitudes	OLLE pre-survey (Q14.a-g); OLLE post-survey	Wave 1 (before primary workshops begin) and Wave 2 (at the final primary workshop)
RQ4	Healthy financial behaviors	The outcome measure is a scale (value range 1-5) calculated as the average of four survey items related to level of agreement with good money management habits	OLLE pre-survey (Q21.a-d); OLLE follow-up survey	Wave 1 (before primary workshops begin) and Wave 3 (one year after program enrollment)

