IVROP ReadyforLIFE Program Evaluation

Statistical Analysis Plan

August 29, 2024

ClinicalTrials.gov ID: NCT05244447

Analysis approach

The main goal of this descriptive study is to assess pre-post change scores in the means of the outcome constructs listed above among program participants before, immediately following, and one year after primary workshops. We will use paired sample t-tests to assess the magnitude and significance of mean score changes among program participants in the analytic sample for each outcome.

The analytic sample for each outcome construct consists of study participants who have a non-missing value at baseline and follow-up time points for that outcome (complete case). The analytic sample may vary by outcome construct based on prevalence of missing data at the baseline, post, or follow-up surveys for those questions. The final report will include descriptive statistics about the sample for each outcome, including which optional services (2.0, PLUS, or none) that participants received. As mentioned in the Outcomes section above, a respondent who answers some but not all survey items in a given outcome construct matrix will have their outcome value assigned as missing if they do not respond to at least 80% of the items in the construct. We will not impute missing baseline or outcome data for our analyses. Findings are considered statistically significant based on $p < 0.05$, two-tailed test. We will adjust our p-values for multiple hypothesis testing and report the adjusted p-values in the appendix of the final report.

As part of data preparation and cleaning, we will check for inconsistent and seemingly inaccurate data. The largest source of potentially inconsistent data that we anticipate is duplicate local evaluation surveys. Participants are able to, and occasionally do, retake the local evaluation surveys on Qualtrics. In the case of duplicate survey data, where participants have taken a local evaluation survey more than one time, we plan to take the following approach:

- Check for incorrectly entered Client IDs that inaccurately flag surveys as duplicates. Using the name and/or DOB fields on the local evaluation survey, we will check that responses that appear to be duplicates were in fact collected from the same participant multiple times (i.e., are true duplicates). If not, we will correct Client IDs as necessary.

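### The protocol's last scoring sentence divides an average by the item count a second time; followed literally, it reproduces none of the six Table 4 ranges

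*Protocol*

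**What the plan says.** Protocol section B.4 (Outcome measures) first says the evaluators will "create a composite measure for each construct by taking an average of the scores on each non-missing item in the construct". It then sets the completeness threshold: "Participants who are missing more than 20% of items for a given construct will be assigned a missing value". This threshold is described as contingent on the final distribution of missing data. The paragraph ends with what reads as the operational instruction for each participant's score: "the average of the relevant survey items will be divided by the number of non-missing values in the construct".

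Table 4 describes six outcome scales, each as an average with a stated range. The nine-item RQ1 measure is a "scale (value range 1-4) calculated as the average of nine survey items", the RQ3 measure a "scale (value range 1-5) calculated as the average of seven survey items" and the RQ4 measure a "scale (value range 1-5) calculated as the average of four survey items". The other three are a three-item RQ1 scale (1 to 5), a five-item RQ2 scale (1 to 4) and a six-item RQ2 scale (1 to 5).

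The SAP (Analysis approach) refers back to the Outcomes section and repeats the completeness rule: an outcome is "assigned as missing if they do not respond to at least 80% of the items in the construct". It gives no scoring formula. It analyses mean change in each score with a paired t-test.

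**The concern.** An average has already been divided by the number of items answered. Dividing it by that number again gives a different quantity, so the two sentences cannot both define the score.

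The second quantity has two defects. It lies off the scale that Table 4 states. It also depends on how many items a person answered: a respondent who skips one item gets a higher score than one who gives the same answers and skips none. In a pre-post comparison, any difference in skipping between waves would then be read as change in attitudes or behaviour.

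The plan itself expects skipping, since the Attrition section of the SAP lists skipped items as a reason for missing outcomes. For the two RQ2 scales the setting also changes. Baseline is taken at the orientation session, while the one-year survey is completed by remote link or by phone (protocol section B.3). Equal skip rates cannot be taken for granted.

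**Working it through.** **Inputs.** Item counts *k* and ranges come from Table 4, and the 20% limit from section B.4. Items are taken to run over the stated range of their scale, as Table 4 implies by calling each scale an average.

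**Formulas.** Let *m* be the number of items answered.
- Rule 1 (plain average): sum / *m*. Range: lowest to highest response.
- Rule 2 (last sentence as written): (sum / *m*) / *m*. Range: lowest / *m* to highest / *m*.
- Permitted skips: the largest whole number not above 0.20*k*. This is 1 for *k* = 9, 7, 6 and 5, and 0 for *k* = 4 and 3.

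**Ranges.** Rule 1 reproduces the plan's figures in all six cases, at every permitted *m*. Rule 2 reproduces none:

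| Scale | Items | Stated range | Rule 2, all answered | Rule 2, one permitted skip | Score ratio *k*/(*k*−1) |
|---|---|---|---|---|---|
| RQ1 beliefs | 9 | 1–4 | 0.11–0.44 | 0.125–0.50 | 1.125 |
| RQ3 financial attitudes | 7 | 1–5 | 0.14–0.71 | 0.17–0.83 | 1.167 |
| RQ2 unhealthy conflict behaviours | 6 | 1–5 | 0.17–0.83 | 0.20–1.00 | 1.20 |
| RQ2 skills | 5 | 1–4 | 0.20–0.80 | 0.25–1.00 | 1.25 |
| RQ4 financial behaviours | 4 | 1–5 | 0.25–1.25 | not permitted | – |
| RQ1 expectations | 3 | 1–5 | 0.33–1.67 | not permitted | – |

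The last two overlap the stated range in part but do not match it. Reading *average* as *sum* in the last sentence turns Rule 2 into Rule 1.

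**Dependence on skipping.** A respondent who answers 3 throughout the five-item scale scores 3/5 = 0.60 with all items answered and 3/4 = 0.75 with one skipped. That is a rise of 25% with the same answers.

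**Where nothing happens to the test.** If everyone answers all items at both waves, Rule 2 divides every score by the same constant, so the paired t statistic and p-value do not change. This always applies to the 3- and 4-item scales under the 20% limit.

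**Shift in the mean when skip rates differ.** The documents give no skip rates, so this part is illustration only. Suppose each item is skipped independently with probability *p*. Among people within the limit, the share with one skip is *w* = *kp* / [(1 − *p*) + *kp*], and the mean inflation factor is 1 + *w*/(*k* − 1).
- *k* = 9: at 1%, *w* = 0.09/1.08 = 0.0833, factor 1.0104. At 2%, *w* = 0.18/1.16 = 0.1552, factor 1.0194. Ratio 1.0089, a shift of +0.89%.
- *k* = 5: at 1%, *w* = 0.05/1.04 = 0.0481, factor 1.0120. At 2%, *w* = 0.10/1.08 = 0.0926, factor 1.0231. Ratio 1.0110, a shift of +1.10%.
- *k* = 7 and *k* = 6 give +0.97% and +1.03%.
- At 1% against 3% the shifts run from +1.66% (*k* = 9) to +2.12% (*k* = 5).

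**Effect on the paired t-test.** This was simulated with no true change, n = 1176 (the protocol's target sample, before the 80% rule), person means around 3 (SD 0.5) and item noise SD 0.6. Responses were rounded and clipped to the scale, and tests were two-sided at 0.05. All inputs except n are assumptions. False-positive rates under Rule 2 across the four affected scales:

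| Item skipping, baseline vs later | Wave-to-wave SD 0 | SD 0.3 | SD 0.5 |
|---|---|---|---|
| 1% vs 2% | 64%–72% | 36%–44% | 24%–27% |
| 1% vs 3% | about 99% | 88%–91% | 62%–75% |

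At 2% against 1% the shift reverses sign, with rates of 23% to 73% over the three SDs. With equal skipping (1% or 2% at both waves) the rate is 4% to 6%. The plain average stays near 5% throughout (3% to 7% across runs).

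**The case against.** The strongest reply is that this is a wording slip that the same page resolves. The opening scoring sentence and all six rows of Table 4 say the score is an average, so one sentence stands against seven statements. The SAP relies on the Outcomes section, which contains Table 4. For harm to follow, an analyst would have to code the odd sentence over the clear ones and overlook that a 1-to-5 scale never exceeds 0.83 or 1.00. Skip rates would also have to differ between waves.

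Most of this is right, and it limits the point: the intended reading is hardly in doubt. It does not remove the need for a correction. The section the SAP relies on contains the faulty sentence as well as Table 4, and that sentence is the one phrased as the step for creating each participant's score.

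The objection to the simulated rates also has force. At 1% against 1.2% skipping the shift is only about 0.2%. The highest rates need identical person means at both waves, which is implausible over a year. With a wave-to-wave SD of 0.8, the rate at 1% against 2% falls to roughly 15% to 20%. The figure of 1176 is tied to the follow-up response target, and no number is given for the Wave 2 outcomes. Item counts are provisional too, because weakly correlated items may be removed; if the five-item scale lost one item, no skip would be permitted and the effect there would vanish. The rates show that the mechanism can matter; they do not predict what will happen in this study.

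**Conclusion.** The concern holds. The outcome-definition paragraph contains two incompatible rules, and the second, as written, matches none of the six stated ranges. This much follows from the documents alone, as do the increases of 12.5%, 16.7%, 20% and 25% per permitted skip on the 9-, 7-, 6- and 5-item scales. Those four scales cover RQ2 and RQ3 and one of the two RQ1 outcomes.

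The finding concerns the text and does not show that the analysis will be wrong. The damage to the tests arises only if the sentence is coded literally and skipping differs between waves; the bias could then go in either direction. For the three-item RQ1 scale and RQ4, only the reported means and mean changes would be wrong, not the p-values. That exemption is provisional, because the 20% threshold may change once the missing data are seen. The correction should be made because the sentence governs every outcome and costs almost nothing to put right.

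**What to change.** In the last sentence of the scoring paragraph in protocol section B.4, replace *average* by *sum*, so that the construct score is the sum of the answered items divided by how many were answered. State the same formula in the SAP beside the 80% completeness rule, so that the score is defined once and without ambiguity. Before analysis, add a check in the code that every score at every wave lies within its Table 4 range; a double division would show at once.

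The cost is one word in the protocol, one sentence in the SAP and a short range check. No new data and no change of method are needed.

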IVROP ReadyforLIFE Program Evaluation

Statistical Analysis Plan

August 29, 2024

ClinicalTrials.gov ID: NCT05244447

Analysis approach

The main goal of this descriptive study is to assess pre-post change scores in the means of the outcome constructs listed above among program participants before, immediately following, and one year after primary workshops. We will use paired sample t-tests to assess the magnitude and significance of mean score changes among program participants in the analytic sample for each outcome.

The analytic sample for each outcome construct consists of study participants who have a non-missing value at baseline and follow-up time points for that outcome (complete case). The analytic sample may vary by outcome construct based on prevalence of missing data at the baseline, post, or follow-up surveys for those questions. The final report will include descriptive statistics about the sample for each outcome, including which optional services (2.0, PLUS, or none) that participants received. As mentioned in the Outcomes section above, a respondent who answers some but not all survey items in a given outcome construct matrix will have their outcome value assigned as missing if they do not respond to at least 80% of the items in the construct. We will not impute missing baseline or outcome data for our analyses. Findings are considered statistically significant based on $p < 0.05$, two-tailed test. We will adjust our p-values for multiple hypothesis testing and report the adjusted p-values in the appendix of the final report.

As part of data preparation and cleaning, we will check for inconsistent and seemingly inaccurate data. The largest source of potentially inconsistent data that we anticipate is duplicate local evaluation surveys. Participants are able to, and occasionally do, retake the local evaluation surveys on Qualtrics. In the case of duplicate survey data, where participants have taken a local evaluation survey more than one time, we plan to take the following approach:

- Check for incorrectly entered Client IDs that inaccurately flag surveys as duplicates. Using the name and/or DOB fields on the local evaluation survey, we will check that responses that appear to be duplicates were in fact collected from the same participant multiple times (i.e., are true duplicates). If not, we will correct Client IDs as necessary.
- Check for completeness. If one duplicate survey is complete while the other is not, we will use the most complete survey to minimize item non-response.
- If both duplicate surveys are equally complete, we will use the first response that a participant submitted, as indicated by the Recorded Date field on the Qualtrics data export.

Raw data sets for baseline, exit, and follow-up survey data will be cleaned and prepared for analyses using the R Studio statistical software package. nFORM survey responses will be downloaded using the Data Export feature of nFORM, and local evaluation survey responses will be exported from Qualtrics. All exports will be imported into R and cleaned separately before data sets are merged into a final, wide format file for analyses using nFORM Client ID as the unique identifier for matching observations.

As a sensitivity check, we plan to repeat the analyses using only participants who received primary workshops (i.e., excluding 2.0 and PLUS participants).

Attrition

The ReadyforLIFE program has consistently exceeded its post-survey and follow-up data collection

participation targets, which has helped to reduce overall sample attrition. This success has been due in large part to strong program completion rates and the follow-up collection strategies that both program and evaluation staff have used with youth participants. Facilitators and life coaches explain the importance of the evaluation at the beginning of the program and inform youth that they will be eligible for a \$50 incentive (a Giftogram gift card redeemable at either Walmart or Target) if they complete the 1-year follow-up survey. This message was reinforced by program alumni in schools who verified that they received their incentives after completing the survey.

Midwest Evaluation and Research employs a dedicated survey tracking team that begins reaching out to eligible participants one month before their 1-year follow-up survey is due, using the contact information collected by program staff during the enrollment process. Participants are eligible for a follow-up survey if they have parental consent and youth assent to be part of the study and have completed at least one baseline survey, regardless of program completion status or program delivery format. The survey tracking team uses multiple methods of contact (text, email, phone calls, letters, and social media) to reach participants. Youth can take the 1-year follow-up survey online (using a link provided via text, email, or social media, or using a QR code provided via letter), or they can opt to complete a survey over the phone with a survey tracking team member.

Sample attrition is tracked on an ongoing basis as part of the bi-weekly Continuous Quality Improvement (CQI) team meetings that MER and IVROP attend together. If response rates drop below the target of 70%, interventions would be put in place to try to increase response rates; however, this has not been necessary to date, as follow-up response rates are currently over 80%.

At the outcome level, attrition will be reported descriptively in the final report. For each outcome construct, we plan to report the proportion of the sample that is missing for that outcome measure and for what reason (e.g., survey non-response, skipped items, exceeded 20% threshold for item missingness within a construct). We will report descriptive statistics for baseline responses, gender as reported on the Applicant Characteristics Survey (ACS), and age as reported on the ACS to compare those who are and are not in the sample for each outcome.

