IVROP ReadyforLIFE Program Evaluation

Study Protocol

ClinicalTrials.gov ID: NCT05244447

August 29, 2024

Descriptive Evaluation Analysis Plan: "The Evaluation of ReadyforLIFE in Imperial Valley, California"

A. HMRE grant recipient

HMRE grant recipient: Imperial Valley Regional Occupation Program, El Centro, CA

Project lead: [name]

Email address: [contact]

B. Evaluator

Evaluator's organization: Midwest Evaluation and Research, Emporia, KS

Evaluator lead: [name]

Email address: [contact]

Descriptive Evaluation Analysis Plan

The Evaluation of ReadyforLIFE in Imperial Valley, CA

A. Description of the intended intervention(s)

The ReadyforLIFE program aims to support the development of healthy, respectful, nonviolent relationships among youth in the Imperial Valley region of California. The primary curriculum includes courses that provide all youth participants with a general overview of healthy partner and family relationships, healthy attitudes and habits about mental health, and money management. Primary workshops are offered predominantly as in-person, in-school sessions that occur during students' regular school hours, though in-person, after school and virtual, evening formats have also been offered to meet the needs of different students. Additionally, participants receive individualized Life Coaching sessions where they can explore career opportunities, get connected to other resources in the community, discuss future interests, and work with their Life Coach to develop an action plan for achieving future goals. A subset of program participants, selected based on their core programming participation and interest on a first-come first-served basis, subject to funding availability, are eligible to receive additional optional program services, described as 2.0 and PLUS services in the outline below. A summary of program services, including dosage and focal population, can be found in Table 1.

- **Goal 1 - Deliver core curriculum as primary services to all IVROP ReadyforLIFE participants:**

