Participants receive *core curriculum* to develop healthy attitudes (relationship and financial) and skills to engage in healthy partner and family relationship behaviors, but only after receiving an orientation about the IVROP ReadyforLIFE Program and giving program staff informed consent to participate in study activities. Then, primary ReadyforLIFE curriculum is delivered. Primary curriculum, delivered by an IVROP facilitator, includes 12 hours of Relationship Smarts, 3 hours of Mind Matters, and 1 hour of Money Habitudes, for a total of 16 primary workshop hours, typically delivered sequentially over 4-5 weeks. For *in-person, in-school workshops*, the number of sessions and length of the workshop series varies depending on classroom schedules. In-school workshops are provided to students whose teachers have agreed to use classroom time to provide the ReadyforLIFE program to their students. ReadyforLIFE is typically offered as a replacement for instructional time in classes that focus on student health and life skills, such as Freshman Seminar, Success 101, or Intro to Health. For *in-person and virtual workshops* held after school, the delivery schedule is typically as follows:
 - **Relationship Smarts (12 hours total)** – three 2-hour sessions per week for two weeks
 - **Mind Matters (3 hours total)** – two 1.5-hour sessions held within one week, after the conclusion of Relationship Smarts
 - **Money Habitudes (1 hour total)** – one 1-hour session held either in the same week as Mind Matters or the following week, along with the exit session and makeup workshops as needed

Virtual and in-person afterschool workshops are typically attended by students who do not have teachers who are offering the program as part of the regular school day. Virtual, evening cohorts are typically made up of students who have extracurricular afterschool activities that prevent them from attending in-person, afterschool workshops.

- **Goal 2 - Deliver support services to all IVROP ReadyforLIFE participants:**

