Relationship skills workshops	Relationships Smarts Plus curriculum: skill-building for youth to have healthy relationships with committed partners	A total of 12 hours, with two-hour sessions occurring three times per week for two weeks (can vary by classroom schedule for in-person, in-school services)	Group classes provided either 1) in-person, in-school, 2) in-person, after school at IVROP facilities, or 3) virtually after school; two trained facilitators lead every session	At-risk youth (defined as attending a high-need high school or meeting other risk criteria such as membership in a low-income or single parent household) ages 14-18 and enrolled in 9-12th grades
Mental health workshops	Mind Matters curriculum: skill-building that helps youth resolve ACEs to manage emotions and improve their state of mind	A total of three hours, with two 1.5-hour sessions held within one week	Group classes provided either 1) in-person, in-school, 2) in-person, after school at IVROP facilities, or 3) virtually after school; two trained facilitators lead every session	At-risk youth (defined as attending a high-need high school or meeting other risk criteria such as membership in a low-income or single parent household) ages 14-18 and enrolled in 9-12th grades
Economic stability workshops	Money Habitudes curriculum: skill-building that uses personality types to develop better money attitudes and habits	A total of one hour, with one 1-hour session held in the same week as Mind Matters or the following week	Group classes provided either 1) in-person, in-school, 2) in-person, after school at IVROP facilities, or 3) virtually after school; two trained facilitators lead every session	At-risk youth (defined as attending a high-need high school or meeting other risk criteria such as membership in a low-income or single parent household) ages 14-18 and

Components	Content	Dosage and schedule	Delivery	Focal population

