The main data source for this study is surveys of intervention participants. Participants are surveyed at three different time points throughout the study. Two surveys (one nFORM and one local evaluation [OLLE] survey) are collected from participants at each of the first two waves of data collection. Wave 1 (nFORM entrance survey and OLLE pre-survey) of data collection happens during the program orientation session before the first primary workshop session, with make-ups administered as needed until three primary workshops have been received. Wave 2 (nFORM exit survey and OLLE post-survey) of data collection happens at or immediately after the final workshop session, with make-ups administered as needed for up to two weeks after primary workshops end. Wave 3 of data collection (the OLLE follow-up survey) happens one year after program enrollment.

Waves 1 and 2 of surveys are administered online using students' school computers, program tablets, or students' personal devices in the case of virtual cohorts. Paper surveys can be offered if necessary due to technological difficulties or facility restrictions. The link to complete the follow-up survey at Wave 3 is sent to participants via email, text message, and postcard/letter using a QR code. Participants can also complete the survey over the phone with evaluation team staff if they prefer.

Wave 1 of data collection began in June 2021 and will conclude at the end of March 2024. Wave 2 of data collection began in July 2021 and is expected to conclude in April 2024. Wave 3 of data collection began in June 2022 and is expected to conclude in March-April 2025.

The analyses for this study will use data from different survey waves, depending on the outcome. Short-term attitudinal changes will be assessed by comparing outcomes between Waves 1 and 2 (program entry to exit), and longer-term behavioral changes will be assessed by comparing outcomes between Waves 1 and 3 (program entry to follow-up).

A copy of the local evaluation survey codebook will be sent as a separate appendix to this plan.

Table 3. Sources of data to address the research questions

Data source	Timing of data collection	Mode of data collection	Start and end date of data collection
Intervention participants (nFORM entrance survey and OLLE pre-survey)	At the orientation session before the first primary workshop	In-person online survey or remote online survey	June 2021-March 2024

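### The paired t-test treats students' changes as independent although the program is delivered to classes and cohorts, so standard errors and p-values will be too small if changes correlate within a cohort

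*SAP*

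**What the plan says.** The SAP (Analysis approach) names one test: "We will use paired sample t-tests to assess the magnitude and significance of mean score changes among program participants in the analytic sample". Significance is two-tailed p < 0.05, on complete cases. Multiplicity-adjusted p-values go in an appendix, by a method that is not named. The one sensitivity check repeats the analyses without 2.0 and PLUS participants.

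The Protocol (section A) describes grouped delivery:

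- "Primary workshops are offered predominantly as in-person, in-school sessions".
- "In-school workshops are provided to students whose teachers have agreed to use classroom time to provide the ReadyforLIFE program to their students" (Goal 1).
- Other students attend after-school or virtual groups. Table 1 says of all these group classes that "two trained facilitators lead every session"; Table 2 lists five facilitators.

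The two kinds of outcome are collected differently (Protocol B.3). Wave 2, used for the three attitude scales, "of data collection happens at or immediately after the final workshop session". For the three behavior scales, "The link to complete the follow-up survey at Wave 3 is sent to participants via email, text message" or by post, one year after enrollment.

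The data sets are to be "merged into a final, wide format file for analyses using nFORM Client ID as the unique identifier for matching observations". No class or cohort identifier is mentioned. Neither document mentions clustering, an ICC, a design effect, a mixed model or robust standard errors.

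**The concern.** A paired t-test is a one-sample t-test on change scores. Differencing removes stable differences in level between classes. It does not remove a shared change: one class may gain more than another because of its facilitators, its teacher or its schedule. The Protocol itself says that the number of sessions and the length of the in-school series vary with classroom schedules. Where changes are positively correlated within cohorts, the sample holds less information than its head count suggests, and the t-test's standard error is too small.

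At stake are the significance calls and the adjusted p-values, which start from the same unadjusted ones. The sensitivity check uses the same test and cannot reveal the problem. Nor could a reader judge it, since no ICC or cohort-level result is planned.

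The effect is probably larger for the attitude scales, surveyed at or just after the last shared session, than for the behavior scales, answered individually and remotely. That ordering is a judgment; the documents contain no data on it.

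**Working it through.** **The plan's own figure.** Projected enrollment of 1,680 × 0.70 target response = 1,176, which matches Protocol B.2. It is a response-rate product, not a power calculation, so there is no stated power to check. No Wave 2 sample size is given.

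**Inputs from the documents.** n = 1,176 (Wave 3 target); two-sided α = 0.05; response of 70% (target), or 80%, since the SAP (Attrition) says "follow-up response rates are currently over 80" percent.

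**Assumptions.** Analysed students per cohort, m: 10 to 30. The middle cases take 25 enrolled per class: 25 × 0.70 = 17.5 and 25 × 0.80 = 20. ICC of change: 0 to 0.10. Cohorts are treated as a sample of the cohorts that could have been served.

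**Formulas.**

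- Design effect: DEFF = 1 + (m − 1) × ICC
- True SE ÷ reported SE = √DEFF
- True two-sided error = 2 × [1 − Φ(1.96/√DEFF)]
- Corrected p for a reported p = 0.01: 2 × [1 − Φ(2.576/√DEFF)]
- Smallest mean change declared significant, in SDs of change: 1.96 × √(DEFF/1,176)
- Change detectable with 80% power: (1.96 + 0.8416) × √(DEFF/1,176)

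**Middle case, m = 17.5.** For example, at ICC 0.05, DEFF = 1 + 16.5 × 0.05 = 1.825, √DEFF = 1.35, and 1.96/1.35 = 1.45, so the error is 14.7%.

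| ICC of change | DEFF | SE ratio | True error | Reported p = 0.01 becomes | Significance threshold (SD) |
|---|---|---|---|---|---|
| 0 | 1.000 | 1.00 | 5.0% | 0.010 | 0.057 |
| 0.01 | 1.165 | 1.08 | 6.9% | 0.017 | 0.062 |
| 0.02 | 1.330 | 1.15 | 8.9% | 0.026 | 0.066 |
| 0.05 | 1.825 | 1.35 | 14.7% | 0.057 | 0.077 |
| 0.10 | 2.650 | 1.63 | 22.9% | 0.114 | 0.093 |

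The change detectable with 80% power moves from 0.082 SD under independence to 0.110 SD at ICC 0.05.

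**At m = 20.** The error is 7.2%, 9.5%, 16.0% and 25.0% at ICC 0.01, 0.02, 0.05 and 0.10.

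**Ends of the range.** m = 10, ICC 0.01: DEFF 1.09, error 6.0%. m = 30, ICC 0.10: DEFF 3.90, SE ratio 1.97, error 32.1%.

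**Simulation check.** With n = 1,176, no true change and Poisson cohort sizes averaging 17.5 (8,000 runs per setting), rejection rates were:

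| ICC of change | Paired t-test | Cluster-robust test (CR2, cohorts − 1 df) |
|---|---|---|
| 0 | 4.8% | 4.8% |
| 0.02 | 9.4% | 5.0% |
| 0.05 | 15.3% | 5.4% |
| 0.10 | 24.1% | 5.1% |

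A separate simulation with 59 cohorts of exactly 20 and ICC 0.05 (10,000 runs) gave 15.8% for the t-test and 5.0% for a t-test on cohort means.

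**The case against.** The strongest objection concerns the target of inference. The SAP calls the study descriptive and speaks of changes among participants in the analytic sample. If the aim is the mean change for these students in these classes, shared cohort effects are part of what is estimated, and clustered standard errors may be too wide. That reading is coherent, but it sits poorly with a plan that sets a p < 0.05 rule and adjusts for multiplicity. The inflation figures do need cohorts to be regarded as a sample, and that should be stated.

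The objection on size also has force. No figure in the documents shows that the ICC of change is above zero. The 32% end combines the largest assumed cohort with the largest assumed ICC. At Wave 3, 30 analysed implies about 43 enrolled per cohort at 70% response (30/0.70), so that end could at most suit Wave 2 in large classes. The practical effect is narrow as well: at n = 1,176 and m = 17.5, only mean changes between 0.057 SD and 0.077 SD would lose significance at ICC 0.05.

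Finally, CR2 is not the only remedy: a cohort random effect or a test on cohort means would also serve. Clustering on class does not cover dependence between classes that share a school or facilitators. These points limit the size of the concern and its claim to a single solution. They do not supply the missing allowance.

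**Conclusion.** The concern holds as a conditional statement: the only planned test assumes independence that grouped delivery gives reason to doubt, and nothing in the plan checks or corrects for it. The mean changes are unaffected. Standard errors, p-values and any confidence intervals are exposed.

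Under the middle assumption of 17.5 analysed per cohort, the nominal 5% test has a true error between 6.9% (ICC 0.01) and 22.9% (ICC 0.10). Over the full assumed range the error runs from 5% to 32%, with no inflation at ICC 0. Confidence is high in the mechanism; the size cannot be settled from the documents. Large mean changes would stay significant; small ones might not. It should be fixed before the final analysis, but it does not undermine the descriptive results.

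**What to change.** Keep the mean change as the estimate. Replace the paired t-test with an intercept-only regression of the change score, with standard errors clustered on class or workshop cohort and a small-sample correction (for example CR2 with Satterthwaite degrees of freedom; the simulation above used cohorts minus 1). Take the p-values that enter the multiplicity adjustment, and any confidence intervals, from this model. For each outcome, report the ICC of change, the number of cohorts and the mean number analysed per cohort.

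State in the SAP that a class or cohort identifier will be linked to the Client ID in the merged file. Clustering on service location should be at most a secondary check, because the after-school and Zoom entries in Protocol B.2 are pooled delivery modes rather than schools. Five facilitators are too few for reliable robust standard errors at that level.

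The cost is SAP wording, a small change to the R code and the linkage. Whether the identifier exists must be confirmed first. Protocol B.2 has final analyses beginning in 2025, after the SAP date of August 29, 2024. If the ICC is near zero, results will barely change; otherwise p-values will be somewhat larger and intervals wider.
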